1. INTRODUCTION

Natalizumab (NTZ) is an extremely effective medication in reducing relapses and delaying or reducing sustained disability worseningⁱ. Therefore, NTZ is frequently prescribed in relapsing multiple sclerosis (MS) patients with highly active disease who have failed previous disease modifying therapy (DMT). However, there is increased risk of developing progressive multifocal leukoencephalopathy (PML) in patients infected with John Cunningham virus (JCV) who are being treated with NTZⁱⁱ. Unfortunately, the prevalence of antibodies to the JCV is relatively high, greater than 50 percent of the populationⁱⁱⁱ. The risk of developing PML reduces NTZ use, particularly after 2 years of NTZ exposure when the risk of PML increases^{iv}. Currently, the risk of developing PML is 4.22 per 1000^v. Therefore, NTZ is frequently stopped once a patient demonstrates evidence of JCV exposure by the presence of anti-JCV antibodies. However, the risk of disease progression has been reported to be higher when switching to another disease modifying therapy. In a study of 88 patients who had been treated on NTZ for 2 years were either maintained on NTZ, switched to another DMT, or remained off DMT. The relapse rate was 3.7% in the NTZ group versus 17.8% in the group on another DMT^{vi}. In another trial evaluating transitioning patients to dimethyl fumarate, the risk of relapse was 19.6% at one year.^{vii} Most recently, a multi-center trial was conducted in Sweden evaluating patients switching to rituximab or fingolimod after treatment with NTZ for greater than 6 months. Within 18 months of stopping NTZ, the relapse rate was 17.6% for fingolimod and only 1.8% for rituximab^{viii}.

In addition, there is no consensus on when to restart another disease modifying therapy although evidence suggests beginning treatment within 3 months of the last dose of NTZ^{ix}. Unfortunately, several studies have indicated that approximately a third of patients, within 3-6 months after withdrawal from NTZ, experienced a clinical and/or radiographic relapse^x.

Ocrelizumab (OCR), a humanized monoclonal antibody that selectively binds to, and destroys CD20-expressing lymphocytes (B-cell lymphocytes), has demonstrated robust efficacy in reducing relapse rate with a relative reduction of 46% and 47% respectively in OPERA I and II^{xi}. In addition, OCR treatment compared to interferon-β1a therapy led to a significant reduction in contrast enhancing lesions on MRI especially at 24 weeks, 48 weeks, and 96 weeks of treatment with a relative reduction of 94% and 95% respectively. Disability progression at 12 and 24 weeks were also significantly different between both groups with a relative reduction of 40% at 96 weeks. No evidence of disease activity (NEDA) was present in 48% of patients at 96 weeks. The percentage of patients meeting NEDA in the AFFIRM trial was only 37%^{xii}. Also, the number was more impressive for OCR with 72% of patients meeting NEDA when assessed after 24 weeks^{xiii}.

In OPERA I and II, adverse events were the same between the two groups. Not surprisingly, infusion related reactions were more common with 11 patients stopping OCR. Also, in patients receiving OCR, upper respiratory infections and nasopharyngitis were more common. However, unlike NTZ, OCR use has not been associated with the risk of developing PML in patients with MS. Also, to date, there are no reported cases of PML in patients who have received rituximab for the treatment of MS.

The robust therapeutic efficacy of OCR in the phase III pivotal trials, the absence of evidence of PML risk, and the convenience of fewer infusions, makes it an attractive alternative therapy for patients with MS being treated with NTZ, particularly those with the presence of anti-JCV antibodies. However, patients who are JCV negative will likely also be interested in OCR given the potential risk of a false negative to the JCV virus with the reported rate of sero-conversion at 2 to 3 percent per year^{xiv}.

Given the efficacy and safety data demonstrated in these trials, OPERA I and II, we anticipate that physicians and patients with relapsing MS being treated with NTZ independent of the JCV status would be interested in transitioning to OCR.

However, breakthrough disease is well documented in patients electively coming off NTZ to reduce PML risk. Therefore, conducting a study to determine if patients on NTZ regardless of their JCV status can be transitioned to OCR safely without disease progression is vital.

On March 28, 2017, Roche/Genentech announced FDA approval of OCREVUS ® (Ocrelizumab) for the treatment of adult patients with relapsing or primary progressive forms of multiple sclerosis.

2. OBJECTIVES

2.1 PRIMARY OBJECTIVES

The primary objective of this study is to assess the efficacy of OCR in RMS patients who have been previously treated with NTZ by evaluating relapse rate, progression on MRI and disability progression.

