3. STUDY DESIGN

3.1 DESCRIPTION OF THE STUDY

This is a multicenter, prospective, open-label Phase IV clinical trial. Patients with relapsing forms of MS, ages 18 to 65, who have received a stable dose of NTZ for 12 or more consecutive months, and have been free of relapses, disability worsening or MRI progression 6 months prior to the transition screening visit will be eligible for the study. After informed consent to participate has been obtained, the patient will have a neurological exam, EDSS, 3T or 1.5T MRI, MSIS-29 and labs done for the screening visit to determine eligibility. 3T or 1.5T brain MRI with and without contrast will be performed with the standard MS protocol. It is preferred that the MRIs are done on a 3T scanner for this trial, but not required. MRIs will be performed with 3mm slice thickness with no gaps between slices. Patients will receive their first dose of OCR 4 to 6 weeks after the last dose of NTZ. Other baseline measures, including EDSS, MSIS-29, and labs will be performed within 4 weeks of screening. A neurological exam, EDSS, and labs will be performed at month 3, month 6, month 9, and month 12. MSIS-29 will be performed at months 6 and 12. MRIs will be performed at screening to determine

eligibility and at months 3, 6, and 12. All adverse events will be reported to the study sponsor. OCR will not be provided by the study; the medication will be supplied through the patient's commercial pharmacy and billed to the patient or the patient's insurance.

Patients will receive OCR 4-6 weeks after their last infusion of NTZ. OCR 300mg IV will be given on Day 0 and repeated with the same dose on Day 14±2. Patients will then receive OCR 600mg IV every 24 weeks.

If discontinuation of study drug occurs, the subject may continue in the trial for observational purposes. If willing to continue, they will complete all visit items moving forward, with the exception of study drug dosing and pregnancy testing (if applicable). If study drug is discontinued and the subject is unwilling to continue in the trial, a premature termination visit will be completed as soon as possible.

The target enrollment is 50 patients from 5 centers. Serious adverse events recorded during the trial will be reported to the study sponsor via Medwatch form.

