3.3 OUTCOME MEASURES

3.3.1 Primary Outcome Measure

The primary endpoint is the proportion of relapse-free patients at month 12 after switching from NTZ to OCR.

Relapse is defined as:

Protocol: Ocrelizumab Providence Health & Services

Page 5 of 34 ML39655

- Occurrence of new or worsening neurological symptoms attributable to MS
- Symptoms persisting for > 24 hours
- Symptoms not attributable to confounding clinical factors (e.g., fever, infection, injury, adverse reaction to medication)
- Symptoms immediately preceded by a stable or improving neurological state for at least 30 days
- Symptoms accompanied by objective neurological worsening consistent with an increase of at least half a step on the EDSS scale, or 2 points on one of the appropriate FSS, or 1 point on 2 or more of the appropriate FSS; the change has to affect the selected FSS (i.e. pyramidal, ambulation, cerebellar, brainstem, sensory, or visual)

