3.3.2 Secondary Outcome Measures

- Proportion of relapse free patients at months 3, 6, and 9
- Annualized Relapse Rate (ARR)
- Mean time to first relapse on OCR
- Proportion of patients free from MRI evidence of MS disease activity at months 3, 6, and 12
- Proportion of patients with new or enlarging T2 lesions at 3, 6, and 12 months. For patients with new or enlarging lesions, the number of new and enlarging lesions
- Proportion of patients with new Gd+ lesions at months 3, 6, and 12. For patients with new Gd+ lesions, number of new Gd+ lesions detected at months 3, 6, and 12.
- Change in the EDSS score from baseline to month 12.
- Change in MSIS-29 from baseline to months 6 and 12
- Number and type of AEs and SAEs
- Proportion of patients that discontinued OCR

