ARR will be analyzed with a Poisson or negative binomial analysis with the total number of relapses as a dependent variable and the logarithm of time followed as an offset. The number of new or enlarging T2 and Gd+ lesions at 3, 6, 9, and 12 months will be summarized and reported. The mean and median change in EDSS from baseline will be determined at 12 months and tested by Wilcoxon signed-rank tests. The mean and median change in MSIS-29 from baseline will be determined at 6 and 12 months and tested by Wilcoxon signed-rank tests.

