4.9.5 Missing Data

Demographic information and baseline disease for patients who followed protocol and completed the study, violated protocol, and discontinued the study will be reported separately and compared. The reasons for discontinuing or violating protocol and the patient's time on drug at occurrence will be reported and any influence on the trial results will be discussed. To assess the comparability between centers, summaries will be reported for all patients overall and by study center. Any other irregularities that result in missing data will be fully identified and discussed.

For the per protocol and full analysis sets, missing data due to discontinuation will be incorporated as censored time points in the survival analysis of relapse-free patients and ARR will be calculated using the range of time that the individual was in the study. If interim time points at 3, 6, or 9 months are missing, only the time points available will be used in the survival analysis. No relapse data will be missing at baseline, since only patients relapse free for six months are included. For the Kaplan Meier analyses and

log rank tests stratified by age, gender, EDSS, and center, we expect these patient characteristics to be non-missing. However, if they are missing, a complete case analysis per variable will be used and the number of missing will be reported.

For the analysis of the change in EDSS and MSIS-29, a complete case analysis with per protocol patients will be used.

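### Disability progression is part of the primary objective, but the only planned disability analysis is EDSS change at month 12, which neither counts patients who progress nor can exclude progression

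*Combined protocol and SAP*

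**What the plan says.** Section 2.1 (Primary Objectives) sets out to assess efficacy "by evaluating relapse rate, progression on MRI and disability progression". The Introduction gives as the study's purpose to learn whether patients can be "transitioned to OCR safely without disease progression".

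The endpoints and analyses that follow are:

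- **Primary endpoint (3.3.1).** Relapse only: "The primary endpoint is the proportion of relapse-free patients at month 12 after switching from NTZ to OCR". Section 4.9.6 sizes the trial on this endpoint alone.
- **Disability outcome (3.3.2, repeated in 4.9.3).** One item: "Change in the EDSS score from baseline to month 12".
- **Disability analysis (4.9.3, Secondary Analysis).** "The mean and median change in EDSS from baseline will be determined at 12 months and tested by Wilcoxon signed-rank tests".
- **Patients analysed (4.9.3 and 4.9.5).** The EDSS analysis is restricted to patients who followed protocol and did not discontinue. Section 4.9.5 adds: "For the analysis of the change in EDSS and MSIS-29, a complete case analysis with per protocol patients will be used". The full analysis set in 4.9.3 is assigned to the relapse endpoints only.
- **Collection (3.1).** "A neurological exam, EDSS, and labs will be performed at month 3, month 6, month 9, and month 12". EDSS is also recorded at baseline, at premature termination and at unscheduled visits (4.5.1 and Appendix A).

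No section defines EDSS progression by size or by confirmation, and none plans a count, a proportion or a time to progression.

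**The concern.** Progression is something that happens to individual patients. A mean or median change is a group summary in which improvers offset worseners, and the median stays at zero as long as most patients do not change. The planned analysis therefore leaves the share of patients who progressed unreported.

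The other two components of the primary objective are handled differently. Relapse has a relapse-free proportion. MRI has proportions free of activity and with new lesions. Disability is the only component without a patient-level measure.

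Other uses of EDSS do not fill the gap. In the relapse definition (3.3.1) an EDSS or functional-system change only supports an acute episode, so worsening without a relapse is not counted. In the Kaplan-Meier analysis EDSS is a grouping variable. MSIS-29 is assigned to quality of life (2.2).

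The choice of patients adds to the problem. If patients who worsen tend to stop early, they drop out of the only disability analysis, although EDSS is recorded at the premature termination visit.

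At stake is one of the three components of the primary objective, in a trial that already collects the data needed to address it.

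**Working it through.** **The plan's own figure.** No sample size, power or precision is given for EDSS. The only figure is for relapse (4.9.6): proportion 0.80, lower limit 0.68, 45 patients, 50 after 10% attrition. With a two-sided 95% Wald interval, n = 1.96² × 0.80 × 0.20 / 0.12² = 42.7, so 43, within two patients of the stated 45. At n = 45 the lower limit is 0.80 − 1.96 × √(0.16/45) = 0.683. Attrition: 45/0.90 = 50. The figure reproduces approximately but says nothing about disability. I use n = 45 below as the number of completers.

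**Constructed example.** Of 45 patients, 5 change by +1.0, 10 by −0.5 and 30 by 0.

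- Mean: (5 × 1.0 − 10 × 0.5)/45 = 0. Median: 0.
- Signed-rank test, zeros dropped, 15 non-zero values: the ten 0.5s share rank 5.5 and the five 1.0s share rank 13. W+ = 5 × 13 = 65; W− = 10 × 5.5 = 55; expected value 15 × 16/4 = 60.
- Variance: 15 × 16 × 31/24 = 310, less the tie correction (990 + 120)/48 = 23.1, giving 286.9. z = 5/√286.9 = 0.295, p = 0.77.
- Other treatments of zeros give p = 0.34 to 0.41, still non-significant.
- Proportion worsening by 1.0: 5/45 = 11.1%, exact (Clopper-Pearson) 95% CI 3.7% to 24.1%.

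**Without any improvers.** If 5 of 45 worsen by 1.0 and nobody else changes, the exact signed-rank p is 2/2⁵ = 0.0625 and the normal approximation gives 0.025. The plan does not say which version is used.

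**Over a range of assumptions.** The documents give no EDSS standard deviation and no expected rate of worsening, so these inputs are assumed: n = 45; progressors change by +1.0 or +1.5; improvers are the mirror image; 20% or 40% of the rest vary by ±0.5; 2,000 simulated trials per scenario.

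| Progress | Improve | Trials with p < 0.05 |
|---|---|---|
| 10% | 10% | about 6% |
| 20% | 20% | 5–6% |
| 20% | 10% | about 20% |
| 10% | 0% | 36–47% |
| 20% | 0% | 83–91% |

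The median change was 0 in about 97% or more of trials in every scenario. The test responds to a net shift. It has little or no power when improvement offsets worsening, and no result from it gives the frequency of progression.

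**What a proportion would give.** Exact 95% intervals at n = 45:

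- 0 events: upper limit 1 − 0.025^(1/45) = 7.9%
- 2 events: 4.4% (0.5% to 15.1%)
- 5 events: 11.1% (3.7% to 24.1%)
- 9 events: 20.0% (9.6% to 34.6%)

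At n = 50, 0 events gives an upper limit of 7.1%, and 5 events give 10.0% (3.3% to 21.8%).

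**Whether the schedule supports confirmation.** Post-baseline visits fall on Days 84, 168, 252 and 336, so worsening first seen by Day 252 can be confirmed at the next scheduled visit, nominally 84 days later. With ±14 days on each visit, the gap runs from 56 to 112 days. Worsening first seen on Day 336 cannot be confirmed within the trial.

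**The case against.** The strongest reply is that the operative text makes disability secondary. Sections 3.3.1, 4.9.3 and 4.9.6 set a single primary endpoint, relapse-free at month 12, and EDSS change is a recognisable secondary outcome. The mismatch could be removed by rewording 2.1, and a confirmed-worsening endpoint would have few events. This stands as a limit on how serious the point is. It does not remove it: while 2.1 names disability progression, nothing in the plan measures it.

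Four stronger readings are tempting, and the documents do not support them.

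- **That the planned test cannot detect worsening.** It can detect a net shift: with 20% progressing and none improving it was significant in 83–91% of simulated trials.
- **That the report would hide all worsening, or would lack a confidence interval.** Section 4.9.3 plans the standard deviation and range, and two-sided confidence intervals for all analyses. In the example the table would show an SD of about 0.41 (√(7.5/44)) and a range of −0.5 to +1.0. A full-point worsening would be visible, but its frequency would not.
- **That the sponsor intends to read a non-significant p-value as stability.** No section says so. The caution concerns what the test can support.
- **That the Introduction's broader question goes unanswered.** Section 3.2 ties breakthrough disease to clinical and radiographic change, and the relapse and lesion endpoints address that. Only the disability component of 2.1 lacks an event measure.

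It is also fair to say that the example was built to cancel exactly and that the documents do not suggest 22% of patients would improve. It shows what is possible, not what is expected; the table gives the range.

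**Conclusion.** The point holds in a limited form. Disability progression is named in the primary objective, yet the plan neither defines it nor counts it. The single EDSS analysis can reveal a net group shift but cannot give the proportion who progressed or exclude progression. It also omits patients who discontinue and leaves the month 3, 6 and 9 scores unused for disability.

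Size: with 45 completers, 11% worsening by a full point (exact 95% CI 3.7% to 24.1%) is compatible with zero mean change, zero median change and p = 0.77. This rests on an assumed pattern of change, because the documents give no EDSS variability or progression rate. The gap between objective and analysis needs no assumption; it follows from the text.

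This should be corrected, but it does not threaten the main result: the relapse-based primary endpoint and its sample size are unaffected.

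**What to change.** Add one secondary endpoint to 3.3.2 and 4.9.3: the proportion of patients, with an exact 95% CI, whose EDSS worsens from baseline at month 3, 6 or 9 and is still worse at the next scheduled visit. The sponsor should fix the size of the worsening in advance; at least 1.0 point is one example.

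- **Analysis set.** Use the full analysis set, including patients who discontinue. Use the premature-termination EDSS, and the scheduled EDSS of those who stop the drug but stay under observation (3.1). State the denominator, and how patients who leave without worsening are counted.
- **Unconfirmed worsening.** Report separately worsening first seen at month 12, worsening seen at termination, and worsening whose confirmation visit was missed.
- **Existing analysis.** Keep the Wilcoxon analysis as a supportive summary. Section 4.9.3 already covers its confidence interval.

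The cost is SAP wording and one table, with no new visits or data. The downside is few events and a wide interval, as the 7.9% upper limit for 0 of 45 shows. If the sponsor does not want this endpoint, the alternative is to take disability progression out of the primary objective in 2.1 and describe the EDSS analysis as change in score only.

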2.2 SECONDARY OBJECTIVES

The secondary objectives of this study are to assess the effect of OCR on quality of life at months 6 and 12 using Multiple Sclerosis Impact Scale (MSIS-29) and to assess safety and tolerability of OCR in patients previously treated with NTZ by evaluating adverse events and discontinuation.

3. STUDY DESIGN

3.1 DESCRIPTION OF THE STUDY

This is a multicenter, prospective, open-label Phase IV clinical trial. Patients with relapsing forms of MS, ages 18 to 65, who have received a stable dose of NTZ for 12 or more consecutive months, and have been free of relapses, disability worsening or MRI progression 6 months prior to the transition screening visit will be eligible for the study. After informed consent to participate has been obtained, the patient will have a neurological exam, EDSS, 3T or 1.5T MRI, MSIS-29 and labs done for the screening visit to determine eligibility. 3T or 1.5T brain MRI with and without contrast will be performed with the standard MS protocol. It is preferred that the MRIs are done on a 3T scanner for this trial, but not required. MRIs will be performed with 3mm slice thickness with no gaps between slices. Patients will receive their first dose of OCR 4 to 6 weeks after the last dose of NTZ. Other baseline measures, including EDSS, MSIS-29, and labs will be performed within 4 weeks of screening. A neurological exam, EDSS, and labs will be performed at month 3, month 6, month 9, and month 12. MSIS-29 will be performed at months 6 and 12. MRIs will be performed at screening to determine

eligibility and at months 3, 6, and 12. All adverse events will be reported to the study sponsor. OCR will not be provided by the study; the medication will be supplied through the patient's commercial pharmacy and billed to the patient or the patient's insurance.

Patients will receive OCR 4-6 weeks after their last infusion of NTZ. OCR 300mg IV will be given on Day 0 and repeated with the same dose on Day 14±2. Patients will then receive OCR 600mg IV every 24 weeks.

If discontinuation of study drug occurs, the subject may continue in the trial for observational purposes. If willing to continue, they will complete all visit items moving forward, with the exception of study drug dosing and pregnancy testing (if applicable). If study drug is discontinued and the subject is unwilling to continue in the trial, a premature termination visit will be completed as soon as possible.

The target enrollment is 50 patients from 5 centers. Serious adverse events recorded during the trial will be reported to the study sponsor via Medwatch form.

3.2 RATIONALE FOR STUDY DESIGN

The clinical data from OPERA I and II demonstrated a highly efficacious medication with a significant reduction in relapses, MRI progression, and disability progression. In addition, the data suggest that OCR is well tolerated as only 3.2% of patients withdrew secondary to side effects in OPERA I and 3.8% of patients withdrew in OPERA II. From a safety perspective, no opportunistic infections were seen in the clinical trials, and this includes PML.

NTZ is a highly effective medication for treating patients with relapsing MS. However, despite adequate disease control and JCV status, patients will eventually discontinue secondary to the potential risk of PML^{xv}. Unfortunately, multiple studies have demonstrated an increase in risk of disease progression after switching to another agent after discontinuing NTZ^{xvi, xvii, xviii}. So, given the robust clinical data and safety profile from the pivotal OCR trials, this medication is an attractive option for patients and clinicians.

In this clinical trial, patients will receive the FDA approved dose and frequency of OCR. In the RESTORE trial, NTZ concentrations reached undetectable levels 8 weeks after the last infusion. Also, data from several clinical trials including STRATEGY and SWITCH suggest that a shorter washout period will reduce the risk of disease recurrence^{xix}. Therefore, OCR will be infused at a minimum of 4 weeks after the last dose of NTZ and up until 6 weeks.

Measuring breakthrough disease to date is best evaluated by measuring clinical and radiographic changes. A patient outcome measure, MSIS-29, will help evaluate changes in quality of life after transitioning to OCR.

